8.1. Demographic and Baseline Characteristics

The following information pertaining to the participant will be obtained from the participant's mother at screening:

- Participant's sex, race, ethnicity, date of birth (including day, month, and year), and whether the delivery was a C-section.
- Participant's gestational age in weeks, if known, and the participant's birth weight (in kilograms). This information may be obtained from the hospital medical record if necessary.
- The mother's age will be obtained whenever possible.
- The participant's mother will be asked about breast-feeding practices from the time of the participant's birth, and planned feeding practices during the study (and this information will be captured in the case report form).

A full medical history and full physical examination will be performed at the screening visit (refer to Section 8.3.1). The participant's anthropometric measurements will be taken at the screening visit and at other specified timepoints in the SoA (refer to Table 2 and Section 8.3.1) for more details).

If the eligibility criteria are met, the participant will be enrolled into the study on Day 1. After enrollment, an estimation of socioeconomic status will be obtained if possible.

Hospital discharge to home, or to nutritional rehabilitation unit, will be collected on Day 1 and obtained from either the participant's parent(s)/legal guardian, or the hospital medical record. The anthropometric measurements obtained at Day 1 will be considered baseline for the purposes of statistical analyses (refer to Section 9.2).

8.2. Efficacy Assessments

Efficacy assessments include calculation of the WAZ and assessments for re-hospitalizations for acute non-surgical illness at various time points per SoA (Table 2).

Refer to Section 9.7 for analyses.

8.3. Safety Assessments

Safety assessments include SAEs and AEs from the time the ICF is signed through Day 90 (or at the last visit [Discontinuation Visit]), if possible, if participant is discontinued/withdrawn early). Planned time points are provided in the SoA (Table 2).

Any AEs and any SAEs that occur from the time of screening until Visit 1 may be obtained from the participant's hospital records.

Refer to Section 8.4 for details regarding AEs and SAEs.

Refer to Section 9.7.1 for analyses.

8.3.1. Medical History and Full Physical Examination

A full medical history, including medications and vaccinations received, will be recorded at screening to assess enrollment eligibility and to provide a baseline.

All conditions that exist before and during screening will be recorded in the medical history. The infant's HIV status, including history of HIV exposure, will also be recorded. Physical examination at screening will include, at a minimum, assessment of all planned anthropometric measurements, including weight to assess WAZ, length to measure WLZ score, MUAC, head circumference, and skinfold thickness. Details regarding standardized anthropometric measurements will be provided in the Study Manual. Presence of bilateral pedal edema will also be assessed.

In addition, resting vital signs, including body temperature (refer to Section 8.3.3) and other assessments of eligibility criteria requiring a physical examination will be performed.

A complete physical examination will include, at a minimum, assessments of the head, eyes, ears, nose and throat, cardiovascular, respiratory, gastrointestinal, musculoskeletal, and neurological systems.

8.3.2. Interim History and Focused Physical Examination

The interim medical history covers the period since the previous clinic visit. If the interim history raises any concerns, a focused physical examination will be conducted as appropriate if indicated by participant's medical issues and will include assessments of body systems involved. AEs identified as a result of the review of the interim medical history should be recorded as outlined in the SoA (Table 2).

8.3.3. Vital Signs

Vital signs, length and weight will be assessed and recorded at all clinic visits.

Vital sign measurements will include pulse rate, pulse oximetry, and body temperature.

Measurements are to be repeated if clinically significant changes are observed or a machine error occurs.

Body temperature should be taken per standard of care at the site. If the participant passes a bowel movement during temperature collection at a clinic visit only, this stool sample should be collected for biomarkers (see Section 8.6).

8.4. Adverse Events, Serious Adverse Events

The definitions of an AE or SAE can be found in Section 10.2.

AEs and SAEs will be assessed as further described in this section and recorded at timepoints indicated in Table 2. The infant's parent(s)/legal guardian will be asked about any event that occurred since the previous clinic or home visit.

The investigator and any qualified designees are responsible for detecting, documenting, and recording events that meet the definition of an AE or SAE and remain responsible for following up AEs that are serious, considered related to the study intervention or study procedures, or that caused the participant to discontinue the study intervention or the study (see Section 7).

The investigator is solely responsible for assessment, including assignment of causality and intensity, reporting and management.

8.4.1. Time Period and Frequency for Collecting AE and SAE Information

All AEs and SAEs will be collected from the time the informed consent is signed through the EoS (Day 90 visit or at the Discontinuation Visit, as applicable). All AEs and SAEs will be classified according to the *Medical Dictionary for Regulatory Activities* (MedDRA).

All SAEs will be recorded and reported to the sponsor or designee immediately within 24 hours, as indicated in Section 10.2.4. The investigator will submit any updated SAE data to the sponsor within 24 hours of it being available.

Investigators are not obligated to actively seek AE or SAE information after conclusion of the study participation. However, if the investigator learns of any SAE, including a death, at any time after a participant has been discharged from the study, and if the investigator considers the event to be reasonably related to the study intervention or study participation, the investigator must promptly notify the sponsor.

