The burden of disease experienced by underweight children is significant, particularly in resource-poor countries. Undernutrition accounts for a global mortality of more than 3 million children every year [World Hunger Organization 2022] and around 45% of deaths among children under 5 years of age, most commonly in LMICs [WHOb 2021]. Underweight infants hospitalized with an acute illness are particularly at high risk of death. A meta-analysis from 23 studies of over 33,000 children under 5 years of age hospitalized with pneumonia found that moderately underweight and severely underweight children (defined in this study as WAZ between -2 and -3 and WAZ less than -3) were 2 and 4.6 times more likely to die, respectively, compared with children of normal weight [Kirolos 2021]. This analysis further estimated that over half of in-hospital child pneumonia deaths in LMICs were attributable to being underweight, with higher deaths in those severely underweight (median 40.9%, range 14.7 to 69.9) compared to those moderately underweight (median 18.3%, range 10.8 to 34.6).

Several studies have reported that in severely underweight children <5 years of age the inpatient and post-hospital discharge mortality rates are similarly high. A study in Bangladesh in children who also had pneumonia demonstrated an in-hospital mortality of 8.6% and mortality of 8.7% within 3 months of discharge [Chisti 2014]. Mortality in severely underweight children hospitalized in Zambia and Zimbabwe for treatment of complicated acute malnutrition was nearly 10% in the year following discharge [Bwakura-Dangarembizi 2021].

Mortality is also high in the subset of underweight children less than 6 months of age. In a study of underweight Kenyan infants less than 6 months of age, in line with what was observed in studies in older children, in-hospital and post-discharge mortality within 1 year were similar (4.9% and 5.3%, respectively) [Mwangome 2017], indicating that these infants remain vulnerable even after acute inpatient management has completed. In the Kenyan study, WAZ was identified as a better predictor of inpatient and post-discharge mortality than some other anthropometric indices traditionally used to assess nutritional status. These findings were reinforced by subsequent studies [Hoehn 2021;Chowdhury 2021] and support that WAZ should be used for early diagnosis of underweight infants and to inform patient management decisions.

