7.2. Participant Discontinuation/Withdrawal from the Study

A participant may withdraw from the study at any time at the request of the participant's consenting parent/legal guardian, or may be withdrawn at any time at the discretion of the investigator for safety, or other reasons. This is expected to be uncommon.

At the time of discontinuing from the study, if possible, an early discontinuation visit should be conducted, and data should be collected, if possible, as shown in the SoA (Table 2). The participant will be permanently discontinued both from the study intervention and from the study at that time.

If the participant's consenting parent/legal guardian withdraws consent for disclosure of future information, the sponsor may retain and continue to use any data collected before such a withdrawal of consent.

If a participant's parent/legal guardian withdraws participant from the study, they may request destruction of any samples taken and not tested, and the investigator must document this in the site study records.

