7.4. Lost to Follow-up

A participant will be considered lost to follow-up if the participant's parent(s)/legal guardian repeatedly fails to return for scheduled visits, whether at the clinic or at home, and is unable to be contacted by the study site.

The following actions must be taken if a participant's parent(s)/legal guardian fails to return to the clinic for a required study visit or is not at home when a home visit is scheduled, and the parent(s)/legal guardian cannot be found for the home visit:

The site must attempt to contact the participant's parent(s)/legal guardian and reschedule the missed visit as soon as possible and counsel the participant's mother on the importance of maintaining the assigned visit schedule and ascertain whether the participant's mother wishes to and/or should continue in the study.

Before a participant is deemed lost to follow-up, the investigator or designee must make every effort to regain contact with the participant's parent(s)/legal guardian (where possible, 3 telephone calls and, if necessary, a certified letter to the participant's parent(s)/legal guardian last known mailing address or local equivalent methods). These contact attempts should be documented in the participant's medical record.

Should the participant's parent(s)/legal guardian continue to be unreachable, the participant will be considered to have withdrawn from the study.

If the participant's parent(s)/legal guardian is unreachable when the weekly doses are being delivered at the home visit, and the doses are not received, the investigator or designee must make every effort to regain contact with the participant's parent(s)/legal guardian (as mentioned above) to deliver the doses.

8. Study Assessments and Procedures

In this study, visits will be comprised of both clinic visits and home visits, as shown in the SoA (Table 2). Home visits and all assessments at these visits will be performed by trained study team staff.

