9.4. Primary Statistical Hypotheses and Sample Size Determination

The primary study hypothesis is that the difference in the mean change from baseline in WAZ is larger for participants randomized to at least 28 days of Bi-26 relative to placebo.

For the sample size calculation for the primary hypothesis, it is assumed that the between_group difference in the WAZ change from baseline is 0.45 with a standard deviation of 1.3. Based on the above assumption(s) using a 2-sided alpha of 5% and a power of at least 90%, a total of 354 participants, 177 in each group, is required.

Assuming a 10% loss to follow-up and a 3% mortality rate, a sufficient number of participants will be screened to ensure approximately 396 randomly assigned participants are enrolled, 198 in each treatment group.

Figure 2: Sample size sensitivity

N/group, 1-sided α =2.5%, Power=90%

9.5. **Populations for Analyses**

For purposes of analysis, the following populations are defined:

- Intention-to-treat (ITT) population: All participants randomly assigned to study intervention.
- **Modified intention-to-treat (mITT) population**: All participants randomly assigned to study intervention, who received at least one dose (including a partial dose) of the study intervention. Participants will be analyzed according to the intervention they were randomized.
- **Per-Protocol (PP) population**: All participants randomly assigned to study intervention, who received the study intervention, have a Day 90 visit, and did not substantially deviate from the protocol procedures. Participants will be analyzed according to the intervention they actually received. Details of criteria for defining the PP population will be specified in the Statistical Analysis Plan (SAP). The inclusion of participants in the PP population will be determined prior to unblinding the study. A participant data listing and a table with protocol deviations will be presented.
- **Safety population**: All participants randomly assigned to study intervention, who received any dose, including a partial dose, of the study intervention. Participants will be analyzed according to the intervention they actually received.

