associated with the date will also be displayed. The same listing will be presented for SAEs but will also include seriousness criteria.

11.6.2 **Deaths**

The death participant listing will include date and time of death, whether the condition under study contributed to death, primary cause of death and autopsy findings (if applicable).

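### Protocol 8.4.1 lets a death before Day 90 go unreported once an infant has left the study, unless it is judged related, so deaths within the stated safety period can be missed

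*Protocol*

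**What the plan says.** **When collection ends.** Protocol 8.4.1 collects all AEs and SAEs from consent "through the EoS (Day 90 visit or at the Discontinuation Visit, as applicable"). Protocol 8.3 and SAP 11.6.1 repeat the earlier cut-off for infants who leave before Day 90.

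**What happens afterwards.** The same section states: "Investigators are not obligated to actively seek AE or SAE information after conclusion of the study participation". If the site does learn of an SAE, expressly including a death, after the infant has been discharged from the study, the duty is conditional: "if the investigator considers the event to be reasonably related to the study intervention or study participation, the investigator must promptly notify the sponsor".

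**Who has left the study.** For withdrawal, Protocol 7.2 says: "The participant will be permanently discontinued both from the study intervention and from the study at that time". For loss to follow-up, Protocol 7.4 says that should the guardians "continue to be unreachable, the participant will be considered to have withdrawn from the study". By contrast, Protocol 7.1 keeps infants who only stop the intervention in the study for safety and weight.

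**What the analysis covers.** Protocol Table 1 sets the safety endpoint as AEs and SAEs through Day 90. The AE overview table in SAP 11.6.1 covers Day 1 through Day 90 in the Safety population and has one row for serious treatment-emergent events with a fatal outcome. SAP 11.6.2 adds a listing: "The death participant listing will include date and time of death" and cause of death. Neither document requires a vital-status check at Day 90 for infants who left early.

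**The concern.** A relatedness condition on events learned of after participation ends is conventional for infants who completed Day 90. Here the same condition also starts at early exit, inside the period the safety endpoint claims to cover. Take an infant withdrawn in week 3 who dies in week 6. If staff hear of it from the family or the hospital, the protocol requires a report only if a blinded investigator thinks the death related.

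What is at stake is the completeness of the death count by arm. The AE overview table has no category for unknown vital status. As described, it does not separate an infant last seen on Day 20 from one known to be alive at Day 90. Leavers may also not be typical: Protocol 7.2 allows the investigator to withdraw an infant for safety reasons, and the Introduction (Section 2) describes this population as remaining vulnerable after discharge. If infants at higher risk leave at different rates in the two arms, the counts would be affected unequally.

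**Working it through.** **1. The plan's own figures.** The documents give no estimate of uncounted deaths. The inputs borrowed here are from Protocol 9.4: about 396 randomised (198 per arm), with "Assuming a 10% loss to follow-up and a 3% mortality rate". For context, the sample size behind them reproduces: a difference of 0.45, SD 1.3, two-sided 5% and 90% power give 176 per arm by the normal approximation and 177 by the t-test (176.3 rounded up), against 177 stated. Inflating 354 gives 354 / 0.87 = 407 or 354 / (0.90 × 0.97) = 406, against 396 stated. The point does not depend on this.

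**2. Does the rule reach deaths before Day 90?**
- Withdrawn infants are off study at once (7.2), and lost infants count as withdrawn (7.4).
- Collection for them stops at the Discontinuation Visit (8.4.1).
- The relatedness condition applies at any time after discharge from the study, with no reference to Day 90.
- So an unrelated death after exit and on or before Day 90 carries no duty to report.

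**3. Scale.** Formula: uncounted deaths = N × proportion lost × share of the 90 days left at exit × mortality × relative risk in leavers.

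Assumptions: the 10% and 3% apply over 90 days (Protocol 9.4 states no horizon), and exit is halfway on average (share 0.5). The relative risk is 1, or 3 as a pessimistic case. The upper mortality scenario is the Introduction's "mortality of 8.7% within 3 months of discharge".

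Infants lost: 396 × 0.10 = 39.6.

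| Mortality | Total deaths | Uncounted, risk ×1 | Uncounted, risk ×3 |
|---|---|---|---|
| 3% | 396 × 0.03 = 11.9 | 39.6 × 0.5 × 0.03 = 0.59 (5%) | 1.78 (15%) |
| 8.7% | 396 × 0.087 = 34.5 | 39.6 × 0.5 × 0.087 = 1.72 (5%) | 5.17 (15%) |

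The percentages agree across rows because mortality cancels: the share is 0.10 × 0.5 × relative risk. If the uncounted deaths are added to the denominator, the ×3 figure is 1.78 / (11.88 + 1.78) = 13%.

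**4. Sensitivity to exit time, at equal risk.** With a quarter of follow-up left and 3% mortality: 39.6 × 0.25 × 0.03 = 0.3 deaths. With all of it left and 8.7%: 39.6 × 1.0 × 0.087 = 3.4 deaths.

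**The case against.** The case against is substantial, and much of it stands.

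- **Small numbers.** The base case is 0.6 deaths over both arms, and the 15% rests wholly on an assumed threefold risk. This stands.
- **Existing safeguards.** While an infant is on study, every SAE, including death, is reported within 24 hours whatever its relatedness. Protocol 7.4 requires repeated missed visits and tracing before loss is declared, and a death found during that tracing is reportable. An SAE still open at the final visit must be followed further (10.2.3), although follow-up may stop at loss and the outcome for analysis is fixed at the final visit. Protocol 10.2.4 lets a site report late SAEs on paper with no relatedness condition. These narrow the gap. None creates a duty to report an unrelated death after exit.
- **Disposition is reported.** SAP 11.1 tabulates withdrawals by treatment, before Day 56 and between Days 56 and 90, with reasons. Unequal exit between arms would be visible. Vital status after exit would not.
- **The 8.7% is a high figure for this trial.** It comes from severely underweight children under 5 who also had pneumonia. For underweight infants under 6 months the same section gives 5.3% within a year. It serves only as an upper scenario.

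A reader might also infer more than the documents support:

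- Dividing 5.2 deaths by 12 would suggest 44%, but that sets a numerator at 8.7% mortality against a denominator at 3%.
- It would be wrong to say that the plan filters deaths in general by relatedness, since the condition applies only after exit.
- Whether the IDMC's review would be biased cannot be judged, because what it sees is set by a charter that is not in these documents.

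**Conclusion.** The concern holds as a gap in a stated rule. Deaths within the Day 90 safety period can go uncounted in infants who withdraw or are declared lost. That they will be undercounted does not follow: it takes an unrelated death between exit and Day 90.

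All-cause mortality is not a named endpoint, and no formal comparison of deaths between arms is planned. Deaths enter through the SAE endpoint, one overview row and a listing. Under the stated assumptions about 5% of deaths are at stake at equal risk and about 15% at triple risk: 0.6 to 1.8 of about 12 deaths, or 1.7 to 5.2 of about 34 in the upper scenario. With about six deaths per arm planned (198 × 0.03 = 5.9), even one or two missing from one arm could change how the by-arm counts read. That justifies a cheap correction, but does not call the design into question.

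**What to change.** **Protocol 8.4.1.** Limit the relatedness condition to events after Day 90 from randomisation. Require any death on or before Day 90 that becomes known to the site to be recorded and reported, whatever its relatedness and whether the infant withdrew or was lost. Make an exception where the guardian has withdrawn consent to further information; Protocol 7.2 already treats that as a distinct step.

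**Data collection.** Add one eCRF field for vital status at Day 90 and date of death. Use the contact attempts already required by Protocol 7.4 to ask whether the infant is alive.

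**SAP 11.1 and 11.6.2.** Add one table by randomised arm: alive at Day 90, died by Day 90, vital status unknown.

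**Cost.** A short protocol amendment with the ethics approval required by Protocol 10.1.1, one eCRF field, one table and slightly more site work. The change recovers only deaths that become known; the unknown column shows how many infants remain unaccounted for.

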8.4.2. Method of Detecting AEs and SAEs

The method of recording, evaluating, and assessing causality of AEs and SAEs and the procedures for completing and transmitting SAE reports are provided in Section 10.2.

Care will be taken not to introduce bias when detecting AEs and/or SAEs. Open-ended and nonleading verbal questioning of the participant is the preferred method to inquire about a SAE occurrence.

Day-to-day fluctuations in chronic conditions that were present at baseline, and do not represent a clinically significant change in the participant's health status will not necessarily be reported as AEs. If the investigator determines that this change is related to the study intervention it will be reported as an AE.

8.4.3. Follow-up of AEs and SAEs

After the initial AE/SAE report, the investigator is required to proactively follow each participant at subsequent visits. All SAEs will be followed until resolution, stabilization, the event is otherwise explained, or the participant is lost to follow-up (as defined in Section 7.4). Further information on follow-up procedures is provided in Section 10.2.3.

